APPENDIX IV: MEDICATIONS ASSOCIATED WITH PROLONGED QTC

The use of the following medications should be avoided during protocol therapy if reasonable alternatives exist. This is not an inclusive list. Because the lists of these agents are constantly changing, it is important to regularly consult frequently updated medical references. For the most current list of medications, please refer to the following reference:

Woosley, RL and Romero, KA, www.Crediblemeds.org, QTdrugs List, Accession Date December 2nd, 2016, AZCERT, Inc. [name]

Medications that prolong QTc		
Amiodarone	Flecainide	
Anagrelide	Fluconazole	
Arsenic trioxide	Haloperidol	
Azithromycin	Ibutilide	
Chloroquine	Methadone	
Chlorpromazine	Moxifloxacin	
Ciprofloxacin	Ondansetron	
Citalopram	Pentamidine	
Clarithromycin	Pimozide	
Disopyramide	Procainamide	
Dofetilide	Propofol	
Domperidone	Quinidine	
Droperidol	Sevoflurane	
Dronedarone	Sotalol	
Erythromycin	Thioridazine	
Escitalopram	Vandetanib	

Medications that	MAY prolong QTc
Aripiprazole	Lapatinib
Bortezomib	Lenvatinib
Bosutinib	Leuprolide
Ceritinib	Mirtazapine
Clomipramine	Nicardipine
Crizotinib	Nilotinib
Dabrafenib	Olanzapine
Dasatinib	Osimertinib
Degarelix	Pazopanib
Desipramine	Promethazine
Dolasetron	Risperidone
Eribulin mesylate	Sorafenib
Famotidine	Sunitinib
Foscarnet	Tacrolimus
Gemifloxacin	Vemurafenib
Granisetron	Venlafaxine
Isradipine	Vorinostat

#### ADVL1515 This protocol is for research purposes only, see page 1 for usage policy

# **APPENDIX V: PHARMACOKINETIC STUDY FORM**

COG Pt ID #

Cycle 1, Day 1 Date:

Please do not write patient names on this form or on samples.

Patient Weight: \_\_\_\_kg Body Surface Area: \_\_\_\_m^2

LY2606368 Dose Level: \_\_\_\_\_mg/m^2 LY2606368 Total Daily Dose: \_\_\_\_\_mg

Blood samples (2 - 3 ml) will be collected in EDTA tubes at the following time points: Day 1 (pre-infusion, 1 hr., 1.5 hrs., 2 hrs., 4 hrs., and 8 hrs. after beginning the infusion), Day 2 (24 hrs. [ $\pm$  2 hrs.] after beginning the Day 1 infusion), Day 5 (96 hrs. [ $\pm$  24 hrs.] after beginning the Day 1 infusion), Day 8 (during CBC evaluation), and Day 15 (pre-infusion and 1 hr. after beginning the Day 15 infusion) of Cycle 1.

Record the exact time the sample is drawn along with the exact time LY2606368 is given on Days 1 and 15.

Blood Sample No.	Time Point	Scheduled Collection Time	Actual Date Sample Collected	Actual Time Sample Collected (24-hr clock)
1	Day 1	Prior to Day 1 LY2606368 infusion	//	
	LY2606368	•	tart Time:	
		End Time:    :	1	
2	Day 1	1 hr. after beginning Day 1 LY2606368 infusion	//	:
3	Day 1	1.5 hrs. after beginning Day 1 LY2606368 infusion	//	_ :
4	Day 1	2 hrs. after beginning Day 1 LY2606368 infusion	//	
5	Day 1	4 hrs. after beginning Day 1 LY2606368 infusion	//	_ :
6	Day 1	8 hrs. after beginning Day 1 LY2606368 infusion	//	_ :
7	Day 2	24 hrs. (± 2 hrs.) after beginning Day 1 LY2606368 infusion	//	:
8	Day 5	96 hrs. (± 24 hrs.) after beginning Day 1 LY2606368 infusion	//	:
9	Day 8	During CBC evaluation	//	
10	Day 15	Prior to Day 15 LY2606368 infusion		
L	Y2606368 Inf	usion on Day 15 Date:// End Time:    :	Start Time:  _	_ _ : _
11	Day 15	1 hr. after beginning Day 15 LY2606368 infusion	//	

One copy of this Pharmacokinetic Study Form should be uploaded into RAVE. A second copy should be sent with the samples to the address listed in Section 8.3.6. See Section 8.3 for detailed guidelines for packaging and shipping PK samples.

Signature:

Date:\_\_\_\_\_

(site personnel who is responsible for research sample collection)

THIS PROTOCOL IS FOR RESEARCH PURPOSES ONLY, SEE PAGE 1 FOR USAGE POLICY

# **APPENDIX VI: TISSUE STUDY FORM (REQUIRED TISSUE)**

COG Pt ID # Please do not write patient names on this form or on samples. Cycle 1, Day 1 Date:

Body Surface Area: \_\_\_\_\_m^2 LY2606368 Total Daily Dose: \_\_\_\_\_mg Body Surface Area: m^2 LY2606368 Dose Level:  $mg/m^2$ 

## **Tumor Sample Labeling:**

Samples should be labeled with the following information:

Protocol number: ADVL1515
Institution:
Patient ID #:
Accession #:
Sample Date:
Site of Acquired Tissue:
Tissue obtained at (check one option below):
Diagnosis DRelapse

## **Shipment of Tumor Tissue:**

Paraffin-embedded tumor specimens must be packaged appropriately and shipped at room temperature to [name] (at the address below). If a tumor block is not available, please send as many scrolls from the tumor block and/or a minimum of 10 unstained slides may be shipped instead. Please indicate above the date of the sample, site of tissue acquisition and whether it was obtained at diagnosis or relapse. Shipments should be sent Monday through Thursday only for priority overnight delivery using the COG FedEx account (do not ship on Friday). One copy of this form should be uploaded into RAVE.

A second copy should be sent with the tissue sample to the lab address below.

Attn: [name]., Ph.D. Phoenix Children's Hospital Center for Cancer and Blood Disorders Room 25117 [name]

\_\_\_\_\_

Notes: \_\_\_\_\_

If this form will be used as a source document, the site personnel who collected the samples must sign and date this form below:

Signature: \_\_\_\_\_

Date:

(site personnel who is responsible for research sample collection)

This protocol is for research purposes only, see page 1 for usage policy  $% \left( {{{\rm{A}}} \right)$ 

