#### 4.1.7.4 Adequate Cardiac Function Defined As:

- Shortening fraction of  $\geq 27\%$  by echocardiogram, or
- Ejection fraction of  $\geq$  50% by gated radionuclide study
- $QTc \le 480 \text{ msec}$

institute of the National Institutes of Health

THIS PROTOCOL IS FOR RESEARCH PURPOSES ONLY. SEE PAGE 1 FOR USAGE POLICY

Note: Patients should avoid concomitant medication known or suspected to prolong QTc interval or cause Torsades De Pointes. If possible, alternative agents should be considered.

Patients who are receiving drugs that prolong the QTc are eligible if the drug is necessary and no alternatives are available. See Appendix IV for drugs that may prolong the QTc.

- 4.1.7.5 Adequate Neurologic Function Defined as:
  - Patients with seizure disorder may be enrolled if on anticonvulsants and well controlled.
  - Nervous system disorders (CTCAE v5) resulting from prior therapy must be ≤ Grade 2 with the exception of decreased tendon reflex (DTR). Any grade of decreased tendon reflex is eligible.
  - For patients with CNS tumors, any baseline neurologic deficit, including seizures, must be stable for at least one week prior to initiating study treatment.
- 4.1.8 Informed Consent: All patients and/or their parents or legally authorized representatives must sign a written informed consent. Assent, when appropriate, will be obtained according to institutional guidelines.
- 4.1.9 Tissue blocks or slides must be sent per Section 8.4 if available. If tissue blocks or slides are unavailable, the study chair must be notified prior to study enrollment.

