#### 8.4.1 Description of Studies

8.4.1.1 CHK 1/2 Expression

Tissue will be collected either from diagnosis or relapse to evaluate CHK1/2 expression in pediatric solid tumors prior to treatment with LY2606368. Tumor tissue will be analyzed by immunohistochemistry.

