#### 8.4.1.2 TP53 Deletion/Mutation

Tissue will be collected either from diagnosis or relapse to evaluate for a deletion and/or mutation of *TP53* by immunohistochemistry and/or sequencing.

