#### 8.4.2 Sample Collection, Handling, and Shipment

Paraffin-embedded tissue blocks or slides will be shipped to [name] at Phoenix Children's Hospital. Detailed instructions regarding collection, handling, and shipping of tissue samples are located in Appendix VI.

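### Appendix VI lets a site send paraffin scrolls alone, whereas 4.1.9, Section 8.1 footnote 7 and 8.4.2 name only blocks or slides and CHK1/2 is to be measured by immunohistochemistry

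*Combined protocol and SAP*

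**What the plan says.** Three places define the archival material as blocks or slides.

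- Inclusion criterion 4.1.9: "Tissue blocks or slides must be sent per" Section 8.4, if available. It continues: "If tissue blocks or slides are unavailable, the study chair must be notified prior to study enrollment". Footnote 7 to the Section 8.1 schedule repeats this notification rule.
- Section 8.4.2: "Paraffin-embedded tissue blocks or slides will be shipped to" the receiving laboratory. The same section then hands the detail to the form: "Detailed instructions regarding collection, handling, and shipping of tissue samples are located in" Appendix VI.

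Appendix VI, under Shipment of Tumor Tissue, is the only place where scrolls appear. Its condition is "If a tumor block is not available", and its instruction is "please send as many scrolls from the tumor block and/or a minimum of 10 unstained slides may be shipped instead".

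On the assays, aim 1.2.2 and Section 8.4.1.1 give one method for CHK1/2: "Tumor tissue will be analyzed by immunohistochemistry". For TP53, Section 8.4.1.2 allows immunohistochemistry, sequencing or both.

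**The concern.** The form that sites are told to follow accepts a material that the sections above it do not name, and that material does not suit the only assay planned for CHK1/2. Immunohistochemistry stains sections mounted on slides. Scrolls are loose, curled sections normally cut for nucleic acid extraction. A site could follow the form exactly and still leave the laboratory with nothing it can readily stain.

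At stake are evaluable patients for secondary aim 1.2.2, and for TP53 as well wherever the laboratory would use immunohistochemistry rather than sequencing. The trial is small, and tissue not requested in the right form at enrollment may be hard to obtain later.

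**Working it through.** No arithmetic applies. The plan states no figure for tissue yield, and the only number in the sentence at issue, the minimum of 10 slides, is not disputed. The check is to set the passages side by side.

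| Place | Material accepted | If it cannot be supplied |
|---|---|---|
| 4.1.9 | Blocks or slides, if available | Notify study chair before enrollment |
| 8.1, footnote 7 | Blocks or slides | Notify study chair before enrollment |
| 8.4, opening text | Archival tissue, form not specified | Notify study chair before enrollment if no tissue |
| 8.4.2 | Blocks or slides | Not addressed; refers to Appendix VI |
| Appendix VI | Block; otherwise scrolls and/or at least 10 unstained slides | Not addressed |

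**Step 1: does the form allow scrolls alone?** The connective and/or admits three shipments: scrolls only, slides only, or both. The minimum of 10 attaches to the slides. No quantity is given for the scrolls. Scrolls only therefore satisfies the sentence as written.

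**Step 2: do the other sections allow it?** 4.1.9, footnote 7 and 8.4.2 do not mention scrolls. The passages differ, and because 8.4.2 sends sites to Appendix VI for detail, the form is the likelier guide to what is shipped.

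**Step 3: does the notification rule close the gap?** Not clearly. Under 4.1.9 the trigger is that blocks or slides are unavailable; under the opening text of 8.4 it is that there is no tissue. A site sending only scrolls would meet the first trigger on a strict reading but not the second. A site that can cut scrolls also has a block to cut from, so it might not regard blocks or slides as unavailable at all.

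**Step 4: which analyses depend on it?**

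| Analysis | Method named | Scrolls alone |
|---|---|---|
| CHK1/2 expression (1.2.2, 8.4.1.1) | Immunohistochemistry only | Not suited |
| TP53 (1.2.3, 8.4.1.2) | Immunohistochemistry and/or sequencing | Usable for sequencing |
| MTD, DLT, pharmacokinetics | No tumor tissue | Not affected |

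The entry for CHK1/2 rests on general laboratory practice. The other entries follow from the documents.

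**The case against.** The strongest reply is that this is a drafting slip with a safeguard already in place. The sentence in Appendix VI is garbled and may never have been meant as a scrolls-only option. The requirement in 4.1.9 is conditional on availability, and the study chair is told when blocks or slides cannot be had. No passage says that scrolls are unsuitable, and a laboratory might mount some of them. Section 11.5 calls the analyses descriptive and exploratory, and Section 2.3.2 presents Chk1 immunohistochemistry as an exploratory look at feasibility.

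Much of this stands, and it limits the size of the point. It does not remove the mismatch. Whatever was intended, sites will act on the words, and the protocol provides no step for mounting scrolls.

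A reader might also infer four stronger things, none of which the documents support:

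- *That blocks or slides are an absolute condition of entry.* 4.1.9 applies only if they are available, so a patient without them can still enroll.
- *That a scrolls-only patient is formally counted as having met the tissue requirement.* No passage defines what counts as met.
- *That a relation between marker and response would be distorted, or that precision falls by a known amount.* Section 11.5 plans no marker-by-response analysis and no interval for marker prevalence. The share of scrolls-only shipments is not given, and not every enrolled patient need have tissue, so any assumed share and base would be arbitrary.
- *That relapse tissue should be preferred to diagnostic tissue.* Section 8.4.1 and the form consistently accept either (8.4.1.2: "Tissue will be collected either from diagnosis or relapse"), and the form records which was sent and the sample date. A preference for the most recent sample would be a reviewer's choice, not the correction of an error.

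**Conclusion.** The point holds as an inconsistency between Appendix VI and Sections 4.1.9, 8.1 (footnote 7) and 8.4.2, with a practical consequence for one secondary aim. Followed as written, the form can yield material unsuited to the only CHK1/2 assay named.

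The size is modest and cannot be put in figures: an unknown number of patients may be lost to a descriptive result. The conclusion rests on two assumptions: that and/or is read literally, and that immunohistochemistry needs slide-mounted sections, which the documents do not state. The correction is worth making because it is specific, protects data the plan intends to collect, and costs almost nothing.

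**What to change.** Reword the sentence in Appendix VI along these lines: *If a block cannot be sent, send a minimum of 10 unstained slides; scrolls may be added for sequencing but do not replace slides.* This brings the form into line with 4.1.9 and 8.4.2, which can stay as they are.

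Add to the form that, when neither a block nor slides can be sent, the existing notification of the study chair before enrollment applies.

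The cost is an edit to one form. Some pathology departments will have to cut slides where they would have cut scrolls, but a department able to cut scrolls from a block should be able to cut slides from it. Patients undergo no new procedure, and no statistical section changes.

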# APPENDIX VII: PHARMACODYNAMIC STUDY FORM

 COG Pt ID #
 Cycle 1, Day 1 Date:

 Please do not write patient names on this form or on samples.

 Body Surface Area:
 m^2

 LY2606368 Total Daily Dose:
 mg

Blood samples (5 ml) will be collected in consenting patients in CPT tubes during Cycle 1 at the following time points: Day 1 (pre-infusion) and Day 2 (24 hrs. after start of Day 1 infusion).

Record the exact time the sample is drawn along with the exact time LY2606368 is given on Day 1.

Blood Sample No.	Time Point	Scheduled Collection Time	Actual Date Sample Collected	Actual Time Collected (24-hr clock)	
1	Cycle 1, Day 1	prior to LY2606368 infusion			
L	LY2606368 Infusion on Day 1         Date://         Start Time:   _  :              End Time:   _  :				
2	Cycle 1, Day 2	24 hrs. after start of Day 1 LY2606368 infusion		_ :	

One copy of this Pharmacodynamic Study Form should be uploaded into RAVE. A second copy should be sent with the samples to the address listed in Section 8.5.6. See Section 8.5 for detailed guidelines for packaging and shipping PD samples.

Record any notes for Sample Storage Conditions below.

Notes:

If this form will be used as a source document, the site personnel who collected the samples must sign and date this form below:

Signature: \_\_\_\_

Date:\_\_\_\_\_

(site personnel who is responsible for research sample collection)

NCI Pediatric Early Phase Clinical Trials Network

A program funded by the National Cancer Institute of the National Institutes of Health

APPENDIX VIII: ISOLATION OF PBMCS AND PLASMA FOR CORRELATIVE STUDIES

[figure not shown]
# Isolation and Storage of Peripheral Blood Mononuclear Cells (PBMCs)

#### a) Purpose

To isolate Peripheral Blood Mononuclear Cells (PBMCs) for long term storage.

## b) Equipment and Material Required

- Whole blood samples to be processed (freshly collected into CPT)
- Cell preparation tubes (CPT)
- Centrifuge (capable of centrifugation at 1,600 × rcf)
- Pipette and tips
- 0.5 ml and 2.0 ml cryo tubes (capable of being stored at -80°C or -150°C)
- Extra collection tubes (to counterbalance during centrifugation)
- 1 x PBS (room temperature)

## c) Procedure

- 1. Gently invert CPT tubes 5 times before placing in the centrifuge
- 2. Counter balance extra collection tubes for centrifugation
- 3. Centrifuge the samples for 20 minutes at 1,600  $\times$  rcf at room temperature

\*\*\*Ensure that tubes will not hit inside of centrifuge rotor once centrifugation begins

- 4. Remove tubes from centrifuge, ensuring that tubes are kept in the upright position so as not to disturb layers.
- 5. Aliquot plasma into labeled 2 ml aliquots, as appropriate (see SOP Processing Blood Samples Step 4 5)
  - \*\*\*Be careful not to disrupt the cell layer while aspirating plasma (see image above)
- 6. Transfer small amount of remaining plasma and cells from CPT tubes into a 15 ml conical tube
- 7. Rinse CPT tubes using 5 ml of  $1 \times PBS$  (gently pipette up and down)

\*\*\*Be careful not to disturb the gel matrix. Rinsing should remove most of the cells from the gel matrix. The wash may be reddish in color.

- 8. Transfer the rinse mixture into the same 15 ml conical tube (one tube per patient sample)
- 9. Discard the rinsed CPT tubes in the biohazard waste
- 10. Bring the total volume, in the 15 ml conical tube, to 15 ml using  $1 \times PBS$

THIS PROTOCOL IS FOR RESEARCH PURPOSES ONLY, SEE PAGE 1 FOR USAGE POLICY

- 11. Mix the cells by gently inverting the tube 5 times
- 12. Centrifuge at  $300 \times \text{rcf}$  for 15 minutes at room temperature
- 13. Aspirate and discard the supernatant, being careful not to disturb the cell pellet
- Add 200-500 μl of PBS to the cell pellet and pipette gently to resuspend pellet (use smallest volume of PBS to fully resuspend pellet)
- 15. Aliquot resuspended cells into 0.5 ml labeled cryo tubes and place in -80°C freezer until shipment.

# **APPENDIX IX: TOXICITY-SPECIFIC GRADING**

# Bilirubin

Grade 1:	≤ 1.5X
Grade 2:	> 1.5X- 3X
Grade 3:	> 3X-10X
Grade 4:	> 10X

ALT: For the purpose of this study, the ULN for ALT is 45 U/L regardless of baseline.

Grade 1:	≤ 135
Grade 2:	136-225
Grade 3:	226-900
Grade 4:	> 900

AST: For the purpose of this study, the ULN for AST is 50 U/L regardless of baseline.

Grade 1:	≤ 150
Grade 2:	151-250
Grade 3:	251-1000
Grade 4:	> 1000

GGT:

Grade 1:	≤2.5X
Grade 2:	> 2.5X- 5X
Grade 3:	> 5X-20X
Grade 4:	> 20X

Institute of the National Institutes of Health

ADVL1515 THIS PROTOCOL IS FOR RESEARCH PURPOSES ONLY, SEE PAGE 1 FOR USAGE POLICY

# **APPENDIX X: CTEP AND CTSU REGISTRATION PROCEDURES**

Food and Drug Administration (FDA) regulations and National Cancer Institute (NCI) policy require all individuals contributing to NCI-sponsored trials to register and to renew their registration annually. To register, all individuals must obtain a Cancer Therapy Evaluation Program (CTEP) Identity and Access Management (IAM) account (https://ctepcore.nci.nih.gov/iam). In addition, persons with a registration type of Investigator (IVR), Non-Physician Investigator (NPIVR), or Associate Plus (AP) (i.e., clinical site staff requiring write access to OPEN, RAVE, or TRIAD or acting as a primary site contact) must complete their annual registration using CTEP's web-based Registration and Credential Repository (RCR) (https://ctepcore.nci.nih.gov/rcr). Documentation requirements per registration type are outlined in the table below.

Documentation Required	IVR	NPIVR	AP	A
FDA Form 1572	•	~		
Financial Disclosure Form	•	~	>	
NCI Biosketch (education, training, employment, license, and certification)	v	`	~	
HSP/GCP training	•	~	~	
Agent Shipment Form (if applicable)	•			
CV (optional)	~	•	•	

An active CTEP-IAM user account and appropriate RCR registration is required to access all CTEP and CTSU (Cancer Trials Support Unit) websites and applications. In addition, IVRs and NPIVRs must list all clinical practice sites and IRBs covering their practice sites on the FDA Form 1572 in RCR to allow the following:

- Added to a site roster •
- Assigned the treating, credit, consenting, or drug shipment (IVR only) tasks in OPEN •
- Act as the site-protocol PI on the IRB approval •
- Assigned the Clinical Investigator (CI) role on the Delegation of Tasks Log (DTL).

Additional information can be found on the CTEP website at <

https://ctep.cancer.gov/investigatorResources/default.htm >. For questions, please contact the RCR *Help Desk* by email at < [contact] >.

Institute of the National Institutes of Health

# **CTSU Registration Procedures**

This study is supported by the NCI Cancer Trials Support Unit (CTSU).

#### **IRB** Approval:

Each investigator or group of investigators at a clinical site must obtain IRB approval for this protocol and submit IRB approval and supporting documentation to the CTSU Regulatory Office before they can be approved to enroll patients. Assignment of site registration status in the CTSU Regulatory Support System (RSS) uses extensive data to make a determination of whether a site has fulfilled all regulatory criteria including but not limited to the following:

- An active Federal Wide Assurance (FWA) number
- An active roster affiliation with the Lead Network or a participating organization
- A valid IRB approval
- Compliance with all protocol specific requirements.

In addition, the site-protocol Principal Investigator (PI) must meet the following criteria:

- Active registration status
- The IRB number of the site IRB of record listed on their Form FDA 1572
- An active status on a participating roster at the registering site.

Sites participating on the NCI CIRB initiative that are approved by the CIRB for this study are not required to submit IRB approval documentation to the CTSU Regulatory Office. For sites using the CIRB, IRB approval information is received from the CIRB and applied to the RSS in an automated process. Signatory Institutions must submit a Study Specific Worksheet for Local Context (SSW) to the CIRB via IRBManager to indicate their intent to open the study locally. The CIRB's approval of the SSW is then communicated to the CTSU Regulatory Office. In order for the SSW approval to be processed, the Signatory Institution must inform the CTSU which CIRB-approved institutions aligned with the Signatory Institution are participating in the study.

## **Requirements for ADVL1515 Site Registration:**

- IRB approval (For sites not participating via the NCI CIRB; local IRB documentation, an IRB-signed CTSU IRB Certification Form, Protocol of Human Subjects Assurance Identification/IRB Certification/Declaration of Exemption Form, or combination is accepted )
- For applicable studies with a radiation and/or imaging (RTI) component, the enrolling site must be aligned to a RTI provider. To manage provider associations access the Provider Association tab on the CTSU website at https://www.ctsu.org/RSS/RTFProviderAssociation, to add or remove associated providers. Sites must be linked to at least one IROC credentialed provider to participate on trials with an RT component. Enrolling sites are responsible for ensuring that the appropriate agreements are in place with their RTI provider, and that appropriate IRB approvals are in place.

